9.4.1.1 Gastrointestinal Prophylaxis

Lansoprazole or other oral proton-pump inhibitor, dosed according to institutional practice, is required to prevent peptic ulcer disease throughout the duration of treatment with dexamethasone.

9.4.1.2 Pregnancy and Contraception

Contraception must continue during study, **during** drug dose interruption intervals, **and** until 30 days (females) or 90 days (males) after the last study drug administration. If applicable, refer to the Country Specific Pregnancy and Contraceptive Supplement (refer to [Appendix K](#)).

If a subject thinks she may be pregnant (e.g., if a menstrual period in an FCBP does not occur at the anticipated time), study drug treatment must be interrupted, and a urine or serum pregnancy test must be performed locally. Study drug administration may resume after documentation of a nonpregnant state.

9.4.2 *RECOMMENDED CONCOMITANT MEDICATIONS*

9.4.2.1 Antiviral Prophylaxis

Valacyclovir (or an equivalent antiviral agent) is recommended for prophylaxis against herpes zoster reactivation.

9.4.2.2 Uric Acid-lowering Agents

Allopurinol or other approved uric acid-lowering agent are recommended for subjects at high risk for tumor lysis syndrome (TLS) due to high tumor burden. Refer to the current [Carfilzomib IB](#) for safety guidance regarding TLS.

9.4.2.3 Mycostatin or Oral Fluconazole

Mycostatin or oral fluconazole may be given to prevent oral thrush throughout the duration of treatment with dexamethasone.

9.4.2.4 Antiemetics and Antidiarrheal Agents

Antiemetics and antidiarrheal agents are recommended for prophylaxis and/or management of treatment-related gastrointestinal symptoms.

9.4.2.5 Thromboprophylaxis

Venous thromboembolism has been observed in patients receiving carfilzomib. Thromboprophylaxis may be considered on the basis of a benefit-risk assessment.

9.4.3 *EXCLUDED CONCOMITANT MEDICATIONS AND THERAPIES*

If an investigator deems that use of an excluded concomitant medication or therapy is required but does not believe that withdrawal from study treatment is indicated, he/she must contact the study medical monitor to determine if continued study treatment is acceptable.

9.4.3.1 Anticancer Agents

Therapy with a marketed or investigational anticancer agent that is not required per this protocol is prohibited, while subjects remain on study treatment, and should be avoided prior to documentation of disease progression.

9.4.3.2 Radiation Therapy

Radiation to large marrow reserves is prohibited; however, focal palliative radiation is allowed with permission from the study medical monitor.

9.4.3.3 Myeloid Growth Factors

Prophylactic use of myeloid growth factors is prohibited, but they may be used for management of neutropenia, in accordance with American Society of Clinical Oncology (ASCO) Guidelines ([Smith 2006](#)).

9.4.3.4 Corticosteroids

Corticosteroids should not be used to treat concurrent medical conditions, unless the dose remains less than the equivalent of 4 mg/day of dexamethasone. Short term use of higher doses may be permitted to treat acute exacerbations of concurrent medical conditions, but this must be discussed with the study medical monitor as soon as is possible.

9.4.3.5 Plasmapheresis

Plasmapheresis is not permitted at any time during the Screening period or while the subject is receiving study treatment. If a subject who has started screening procedures requires plasmapheresis or is anticipated to require plasmapheresis during or after the Screening period, this subject will be considered ineligible.

For subjects requiring plasmapheresis while on study treatment, every attempt should be made to document disease status by IMWG criteria first. Study treatment must be discontinued and the subject will enter LTFU.

9.4.3.6 Novel Agents for Non-neoplastic Conditions

The use of novel agents for non-neoplastic conditions is prohibited throughout the duration of treatment and for 30 days following the last dose of study treatment.

10 STUDY ASSESSMENTS AND PROCEDURES

All protocol-required tests and observations, along with their chronology, are outlined in the Schedule of Assessments (refer to [Appendix A](#)). Protocol-specified assessments and procedures are summarized below.

10.1 STUDY SPECIFIC PROCEDURES

10.1.1 *MULTIPLE MYELOMA HISTORY AND PRIOR LINES OF THERAPY ASSESSMENT*

When documenting prior therapies for multiple myeloma, the following guidelines should be used:

- A new line of therapy is considered to start when a planned course of therapy is modified to include other treatment agents (alone or in combination) as a result of lack of adequate response, PD (even if the level of progression has not yet met IMWG criteria for PD), relapse, or toxicity. A new therapy is also considered to start when a planned period of observation off-therapy is interrupted by a need for additional lines of therapy.
- An increase in treatment administration, with the intention of recapturing response in a patient with evidence of disease progression on that line of therapy, is considered to be a new line of therapy.

Examples of a line of therapy include:

- Induction therapy and stem cell transplant followed by planned maintenance therapy (provided there is no intervening PD)
- Induction therapy followed by maintenance therapy (provided there is no intervening PD)

If available, historical FISH data should be entered into the eCRF. The following results should be captured:

- t(4;14)
- t(6;14)
- t(11;14)
- t(14;16)
- t(14;20)
- Del 17p
- Del 13
- Chromosome 1 abnormalities

10.1.2 VITAL SIGNS

Vital signs will include heart rate, blood pressure, respiratory rate, and temperature and will be assessed at Screening, prior to each administration of carfilzomib, EOT, and as needed to assess potential AEs. Clinically significant abnormal vital signs will be reported as AEs.

10.1.3 COMPLETE PHYSICAL EXAMINATION

A physical examination will be performed during Screening, prior to dosing on Day 1 of each cycle, and at the EOT. For Cycle 1 Day 1, the screening physical examination may be used if performed within 7 days prior to Cycle 1 Day 1. Physical exam may be completed up to 3 days prior to Day 1 of each cycle. At a minimum, the physical exam should include constitutional, abdominal, cardiovascular, and respiratory assessments.

Clinically significant abnormal findings identified after the signing of informed consent must be reported as AEs and examined more frequently, as clinically indicated. Note: Clinically significant abnormal physical examination findings identified prior to the signing of informed consent should be reported as part of Medical History, not as AEs.

BSA is to be determined by a standard formula, such as the Mosteller Formula ([Mosteller 1987](#)): body surface area (BSA) (m²) = ([Height (cm) × Weight (kg)]/3600)^½. Body surface area must be recalculated and used for subsequent dose determinations, if the subject experiences a weight change of ≥ 20%. Recalculations of BSA must be made using the same technique as used at baseline.

10.1.4 EASTERN COOPERATIVE ONCOLOGY GROUP PERFORMANCE STATUS

Eastern Cooperative Oncology Group Performance Status will be assessed at Screening and at the EOT visit. Eastern Cooperative Oncology Group Performance Status grades and descriptions are tabulated in [Appendix E](#).

10.1.5 INTERNATIONAL STAGING SYSTEM STAGE DETERMINATION

Beta-2 microglobulin and albumin will be assessed at the central laboratory during Screening to determine ISS Stage (refer to [Appendix B](#) and [Appendix H](#)). These results must be available, prior to randomization.

10.2 MULTIPLE MYELOMA DISEASE ASSESSMENTS

Disease response and progression assessments include (but are not limited to): SPEP, urine protein electrophoresis (UPEP), immunofixation, SFLC, bone marrow sample evaluation, serum calcium, plasmacytoma evaluation, and skeletal survey. Multiple myeloma assessment should be based on calendar day, regardless of cycle delay. SPEP, UPEP, immunofixation, SFLC, bone marrow evaluation, and serum calcium will all be conducted at the central laboratory.

The following disease assessments must be performed at Screening:

- SPEP, UPEP (24-hour assessment, no substitute method is acceptable), and immunofixation
- SFLC
- Quantitative immunoglobulins
- Beta-2 microglobulin

Cycle 1 Day 1 before treatment begins (Screening values may be used if obtained within 7 days prior to Cycle 1 Day 1), and every 28 days (± 4 days) thereafter, at EOT, and during LTFU if disease progression has not already been documented (every 28 days ± 4 days, until PD and/or started a subsequent antimyeloma therapy):

- SPEP, immunofixation
- UPEP (24-hour assessment, no substitute method is acceptable), and immunofixation: post-Cycle 1 Day 1 measurements required only if Cycle 1

Day 1 UPEP \geq 200 mg/24 hours or to confirm a disease response (for very good partial response [VGPR] or better) or progression (if applicable)

- SFLC: post-Cycle 1 Day 1 measurements required only for SFLC measurable disease or to confirm stringent complete response (sCR)
- Quantitative immunoglobulins

Subjects will be instructed to collect 24-hour urine samples for assessment of UPEP at Screening and as required during the study. This collection will occur over 2 days and will be assessed at the central laboratory. For further instructions, refer to the Central Laboratory Services Manual.

Radiological disease assessments at baseline are collected after subject eligibility is confirmed and may be done after randomization (as long as they are done before the start of treatment). Radiological disease assessments that were done per standard of care within 30 days before Cycle 1 Day 1 can be used as study baseline disease assessments. They include:

Extramedullary Plasmacytoma Assessment

- A plasmacytoma evaluation will be conducted at baseline, only if a lesion is suspected clinically.
- If an extramedullary plasmacytoma is detected, evaluation will be repeated during treatment to confirm a response of PR or better or to assess for PD based on plasmacytoma.
- Plasmacytomas are considered measurable if they have a longest diameter of at least 1 cm and the product of cross diameter measurements is at least 1 cm². Plasmacytomas of lesser size are considered unmeasurable. Bidimensional measurements must be recorded in the designated eCRF. The same technique must be used to evaluate plasmacytomas throughout the duration of study participation and may include: palpation, ultrasound, x-ray, computed tomography (CT) scan, magnetic resonance imaging (MRI), positron emission tomography (PET), or any other technique that is considered to be standard of care.

Skeletal Survey

- Skeletal survey will include lateral radiograph of the skull, anteroposterior and lateral views of the spine, and anteroposterior views of the pelvis, ribs, femora, and humeri. The skeletal survey will be conducted at baseline and will be repeated if worsening clinical symptoms suggest PD, or as clinically indicated.
- Other radiologic modalities for performing skeletal assessment (eg, low-dose CT scan) are acceptable, in accordance with regional standards.

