5 SUBJECT ELIGIBILITY

5.1 INCLUSION CRITERIA

101. Age \geq 18 years
102. Able to provide written informed consent in accordance with federal, local, and institutional guidelines
103. Relapsed multiple myeloma
104. Refractory multiple myeloma, defined as meeting 1 or more of the following:
 - a. Nonresponsive to most recent therapy (stable disease or progressive disease [PD] while on treatment), or
 - b. Disease progression within 60 days of discontinuation from most recent therapy
105. At least 2, but no more than 3, prior lines of therapy for multiple myeloma
106. Prior exposure to an IMiD
107. Prior exposure to a proteasome inhibitor (PI)
108. Documented response of at least partial response (PR) to at least 1 prior line of therapy

109. Measurable disease, with at least 1 of the following assessed at a central laboratory within the 21 days prior to randomization:
 - a. Serum M-protein ≥ 0.5 g/dL
 - b. Urine M-protein ≥ 200 mg/24 hours
 - c. In subjects without measurable serum or urine M-protein, serum free light chain (SFLC) ≥ 100 mg/L (involved light chain) and an abnormal serum kappa:lambda ratio
110. Eastern Cooperative Oncology Group Performance Status (ECOG PS) of 0 or 1
111. Left ventricular ejection fraction (LVEF) $\geq 40\%$ within the 21 days prior to randomization
112. Adequate organ and bone marrow function performed at a central laboratory within the 21 days prior to randomization, defined by:
 - a. Bilirubin < 1.5 times the upper limit of normal (ULN)
 - b. Aspartate aminotransferase (AST) and alanine aminotransferase (ALT) < 3 times the ULN
 - c. Absolute neutrophil count (ANC) $\geq 1 \times 10^9$ /L (screening ANC must be independent of growth factor support for ≥ 7 days)
 - d. Hemoglobin ≥ 8 g/dL (Use of erythropoietic stimulating factors and red blood cell [RBC] transfusions per institutional guidelines are allowed; however the most recent RBC transfusion may not have been done within 7 days prior to obtaining the screening hemoglobin.)
 - e. Platelet count $\geq 50,000$ /mm³ ($\geq 30,000$ /mm³ if myeloma involvement in the bone marrow is $> 50\%$. Subjects must not have received platelet transfusions for at least 7 days prior to obtaining the screening platelet count.)
 - f. Calculated or measured creatinine clearance (CrCl) of ≥ 30 mL/min. Calculation must be based on the Cockcroft and Gault formula:
[(140 – Age) \times Mass (kg) / (72 \times Creatinine mg/dL)]; multiply result by 0.85 if female

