4.2 Planned Covariates

The primary analysis of PFS, ORR and OS will be stratified by the stratification factors at randomization: ISS stage at study entry (Stage 1 versus Stage 2 or 3), refractory to bortezomib treatment (yes versus no), and age ($< 65 \text{ versus} \ge 65 \text{ years}$).

5. Hypotheses and/or Estimations

The inferential comparison of PFS between treatment groups will be made using a log-rank test stratified by randomization stratification variables. The 1-sided p-value from the stratified log-rank test will be compared against the value specified by the alpha spending function specified in Section 8 at the given analysis (interim or final) to test the null hypothesis that weekly arm doesn't have superior PFS than twice weekly arm. The inferential comparison of ORR between treatment groups will be made using a Cochran-Mantel-Haenszel test stratified by randomization stratification variables. The inferential comparison of OS between treatment groups will be made using a log-rank test stratified by randomization stratification variables.

6. Definitions

Anti-myeloma therapies during long term follow-up

Anti-myeloma therapies during long term follow-up will be those therapies entered in the anti-myeloma therapy case report form (CRF) administered during the long term follow-up period of the study.

Baseline

For analyzing progression-free survival time (PFS) and overall survival time (OS), baseline will be defined as the day of randomization.

For the analysis of other endpoints, baseline will be defined as the value measured on day1 of the first cycle of protocol-specified therapy. The protocol specifies that all study procedures on day 1 should be completed before the initiation of protocol-specified therapy, which will be the assumption in the analysis, unless the time of the assessment is recorded. If a day 1 value is not available, the latest value before the day of the start of protocol-specified therapy will be used. If a subject doesn't receive any protocol-specified therapy, then the latest value prior to or on randomization date will be used.

Best overall response

Statistical Analysis Plan: 20140355

Date: 09 Jun 2017 Page 12

Best overall response will be assessed by computational assessment, Independent Review Committee (IRC) and investigator. The primary analysis of ORR will be based on best overall response assessed by computational assessment.

Best overall response by computational assessment

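### Urine disease qualifies a subject on the screening UPEP, but routine urine follow-up hangs on the Cycle 1 Day 1 UPEP, and Section 10.2 conflicts with Appendix B on when UPEP is due

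*Protocol*

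**What the plan says.** **Eligibility.** Protocol Section 5.1, criterion 109, asks for "Measurable disease, with at least 1 of the following assessed at a central laboratory within the 21 days prior to randomization". One of three routes is enough. Route b is "Urine M-protein ≥ 200 mg/24 hours". Route c is open only to subjects with no measurable M-protein: "In subjects without measurable serum or urine M-protein, serum free light chain (SFLC) ≥ 100 mg/L", with an abnormal kappa:lambda ratio.

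**Start of treatment.** Protocol Section 7 puts Cycle 1 Day 1 within 5 calendar days of randomization, or later with the medical monitor's approval.

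**Follow-up in Section 10.2.** Serum electrophoresis, serum immunofixation and immunoglobulins are repeated every 28 days without condition. UPEP is conditional: "and immunofixation: post-Cycle 1 Day 1 measurements required only if Cycle 1" Day 1 UPEP is at least 200 mg/24 h, "or to confirm a disease response (for very good partial response [VGPR] or better) or progression (if applicable". SFLC is also conditional: "SFLC: post-Cycle 1 Day 1 measurements required only for SFLC measurable disease or to confirm stringent complete response (sCR". For the Day 1 sample, "Screening values may be used if obtained within 7 days prior to Cycle 1 Day 1".

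**Other passages.**
- Section 10.3.2: if baseline UPEP is below 200, two UPEPs are needed once SPEP is consistent with a response of PR or better.
- Section 10.3.3: the Appendix B assessments are required to determine PD.
- Appendix B: UPEP and SFLC are marked every 28 days and at EOT with no threshold. Footnote d continues both every 4 weeks in LTFU before progression, again with no threshold. Footnote a refers back to Section 10.2.
- SAP Section 6, Baseline: for endpoints other than PFS and OS, "baseline will be defined as the value measured on day1 of the first cycle of protocol-specified therapy".

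**The concern.** Two different samples decide two linked things. The screening UPEP decides that urine is the subject's measurable disease; the Day 1 UPEP decides whether urine is then followed routinely. No rule in Section 10.2 covers a subject at or above 200 at screening and below 200 on Day 1.

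If urine was the only measurable marker, what remains as unconditional routine follow-up is serum electrophoresis, serum immunofixation and immunoglobulins. The serum M-protein was not measurable at entry, and immunoglobulin levels are not among the Appendix G criteria. The primary analyses of PFS and ORR use ORCA, so a gap in scheduled laboratory data bears on both. SAP Table 1 censors a subject who is alive without PD at the last disease assessment and does not say that this assessment must include the marker on which the subject was enrolled. A subject who attends every visit without a UPEP could be carried as progression-free.

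The UPEP to confirm progression also needs something to raise the suspicion first. In an open-label trial that may be the investigator's decision to order the test.

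**Working it through.** The plan states no figure on this point to reproduce. The check is a reading of windows and triggers, followed by an illustration of size.

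**1. Windows.** Longest interval from screening sample to Day 1: 21 + 5 = 26 days. Re-use is allowed up to 7 days. A sample 8 to 26 days old, 26 − 8 + 1 = 19 possible days, needs a separate Day 1 UPEP, and that value sets the follow-up.

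**2. Triggers for an example subject.** Take urine-only disease, screening UPEP 230, Day 1 UPEP 185 (illustrative values).

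| Trigger for further UPEP or SFLC | Does it start urine follow-up? |
|---|---|
| Day 1 UPEP at least 200 (10.2) | No: 185 |
| Confirm VGPR or better, or progression (10.2) | Only after another finding raises it |
| SPEP consistent with PR or better (10.3.2) | Not reliably: SPEP was not measurable |
| SFLC-measurable disease (10.2) | Does not trigger UPEP; SFLC itself depends on the time point at which the term is read |
| Appendix B grid and footnote d | Yes, with no threshold, but footnote a points back to 10.2 |

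**3. Why serial values matter.** Appendix G defines urine PD as a rise of at least 25% from the lowest value and at least 200 mg/24 h in absolute terms. If Day 1 is the only value, 25% of 185 is 46, so the absolute rule governs and PD needs 185 + 200 = 385. If urine M-protein had in fact fallen to 0, PD would be reached at 0 + 200 = 200. Without serial UPEP the nadir is unknown and the threshold can be set too high by up to 185.

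**4. Chance of crossing 200.** The documents give no within-subject variation. Assume a log-normal error around a stable level equal to the screening value s:

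P(Day 1 < 200) = Φ( ln(200/s) / √ln(1 + CV²) )

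| s (mg/24 h) | CV 20% | CV 30% | CV 50% |
|---|---|---|---|
| 250 | 13% | 22% | 32% |
| 300 | 2% | 8% | 20% |
| 400 | 0% | 1% | 7% |
| 600 | 0% | 0% | 1% |

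The risk sits close to the threshold. Averaged over an assumed population (log-normal urine M-protein, median 500 or 1000 mg/24 h, between-subject log SD 1.0 or 1.3, within-subject CV 15 to 35%; 2,000,000 simulated subjects per scenario), 1.0% to 6.2% of those at or above 200 at screening fall below 200 on a repeat.

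**5. Number of subjects.** The urine-only share is also assumed.
- Share 10 to 20% (46 to 92 of 460), crossing 1.0 to 6.2%: 46 × 0.010 = 0.5 to 92 × 0.062 = 5.7.
- Share 5 to 15%, crossing 5 to 20%: 460 × 0.05 × 0.05 = 1.2 to 460 × 0.15 × 0.20 = 13.8.

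The second upper end applies 20% to every urine-only subject, which suits only values near 200. Neither range is reduced for subjects who re-use a screening value no more than 7 days old and so cannot be affected.

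**The case against.** The strongest reply is that other passages already schedule the test. Appendix B marks UPEP and SFLC every 28 days, footnote d carries both into LTFU, and Section 10.3.3 makes Appendix B required for PD. A site following the grid would collect the samples, and Section 10.2 does not forbid them. This stands as a limit on the consequence. It does not remove the problem: footnote a sends the reader back to the restrictive text, so the documents give two answers.

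Second, the meaning of SFLC-measurable disease is not tied to a time point. On Day 1 the example subject has no measurable serum or urine M-protein. If SFLC is measurable then, Appendix G's free light chain criteria for response and PD can be read to apply. This also stands; it depends on a definition that the protocol does not give.

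Third, PD has other routes: a rise in serum M-component, hypercalcemia, bone lesions, plasmacytoma and marrow. Death is a PFS event in any case. A reader might infer that ORCA would have no marker at all, or that progression could be found only clinically. The documents do not support that, and the ORCA specification is a separate document not available here.

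A reader might also infer that the steroid allowance in criterion 210 lowers Day 1 values. The protocol gives no figure for such an effect, so no weight is placed on it.

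**Conclusion.** The mismatch holds. The screening UPEP governs entry and the Day 1 UPEP governs routine urine follow-up under Section 10.2, with no rule when they fall on opposite sides of 200 mg/24 h. The exposed group is narrow: urine as the only measurable marker, a separate Day 1 sample, and a Day 1 value below 200. For these subjects urine nadir, response and laboratory PD may be missed. The conflict between Section 10.2, Appendix B and Section 10.3.3 exists whatever the number affected. Section 10.3.2 also differs from Section 10.2 and the Appendix G note on whether UPEP confirmation starts at PR or at VGPR.

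The size is small, probably a handful of 460. That rests on an assumed urine-only share and assumed UPEP variation; neither is in the documents. Nothing in the text indicates that one arm would be affected more than the other, so an inference of bias toward either regimen is not supported. This is a clarification worth making, not a threat to the primary comparison.

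**What to change.** 1. **Section 10.2, UPEP:** require it every 28 days if the screening or the Cycle 1 Day 1 UPEP was at least 200 mg/24 h, and keep the existing confirmation triggers.
2. **Section 10.2, SFLC:** require follow-up for any subject who qualified under 109c at screening, or who on Day 1 has measurable SFLC but no measurable serum or urine M-protein.
3. **Alignment:** make Sections 10.2 and 10.3.2 and Appendix B (grid, footnotes a and d) state the same rule, including the response level at which UPEP confirmation starts.
4. **Baseline:** keep the SAP's Day 1 baseline. The screening value should not become the ORCA response baseline. Appendix G accepts a fall below 200 mg/24 h as the urine part of PR, so a subject at 230 then 185 would meet that threshold before any dose.

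Because PD is measured from the lowest value, item 1 restores urine PD detection without a change of baseline. It does not by itself make PR assessable on urine when Day 1 is below 200; item 2 covers those with measurable SFLC. The cost is wording changes and a few extra 24-hour urine collections, which the Appendix B grid already schedules.
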